CRO	contract research organization	
eCRF	electronic case report form	
FDA	Food and Drug Administration	
GCP	Good Clinical Practice	
Hb	hemoglobin	
ICF	Informed consent form	
ICH	International Conference on Harmonisation	
IEC	Independent Ethics Committee	
IRB	Institutional Review Board	
ITT	intent-to-treat	
MedDRA Medical Dictionary for Regulatory Activities		
NCS not clinically significant		
OCRDC Oracle Clinical Remote Data Capture		
PDR	Patient Data Report	
RBC	red blood cell	
SAE	serious adverse event	
SAP	statistical analysis plan	
SCD	sickle cell disease	
TEAE	treatment-emergent adverse event	
t.i.d.	three times daily	
ULN	upper limit of normal	
WHO	World Health Organization	

1 INTRODUCTION

1.1 Background

Pursuant to the Accelerated Approval of Ferriprox by the FDA in October 2011, ApoPharma Inc. committed to conduct a confirmatory trial of Ferriprox (deferiprone) in transfused patients, focusing primarily on those with sickle cell disease (SCD). Study LA38-0411, currently in progress, is a 52-week, prospective, multi-center, 2-arm, randomized, parallel, open-label trial comparing deferiprone therapy to deferoxamine therapy. Once patients in that trial have completed the last study visit (Week 52), they will be invited to enroll in LA38-EXT, a 2-year extension study in which all participants will receive deferiprone.

1.1.1 Sickle Cell Disease

SCD is an inherited hemoglobinopathy determined by combinations of 2 abnormal alleles of the beta globin gene, among which at least one carries the beta6 glu-val mutation. (1) The disease is clinically silent until expression of the gamma genes is substituted by expression of the beta genes, at between 3 and 9 months of age. There is a varied phenotypic expression as a result of diverse genetic and environmental factors.

Hemoglobin is the iron-containing oxygen-transport metalloprotein in red blood cells (RBCs) responsible for tissue oxygenation. Normal RBCs contain mainly hemoglobin A, while individuals with sickle cell conditions have the genetic variation hemoglobin S (HbS). RBCs that contain mostly HbS do not survive as long as normal RBCs; typically about 16 days, compared to about 120 days for normal cells. (1) RBCs containing HbS can become crescent (sickle) shaped, leading to loss of their mobility and flexibility. (2) As a result, they have difficulty passing through small blood vessels. This in turn leads to blood-cell agglomeration, impeding the circulation of blood and delivery of oxygen to vital tissues and organs. (2) Tissue that does not receive a normal blood flow eventually becomes ischemic. (3) The anemia and blockage of blood flow result in a variety of problems, such as sickle cell crisis (severe pain), susceptibility to infection, priapism, skin ulcers, acute chest syndrome, acute splenic sequestration, pulmonary disease, renal and hepatic dysfunction, and cerebrovascular disease, ultimately causing premature death. (3,4) Abnormal cardiac findings, with the notable development of a progressive proliferative systemic vasculopathy, pulmonary hypertension, and left ventricular diastolic dysfunction, are also present in most patients with SCD and are primarily the result of chronic anemia, cardiac chamber dilation, and compensatory increase in left and right ventricular mass. (5,6)

Some SCD patients undergo transfusions to improve blood rheology by replacing sickled RBCs with normal RBCs. Blood transfusions have been indicated for the prevention and treatment of vaso-occlusive complications such as painful crisis, stroke, acute chest syndrome, acute multi-organ failure, acute splenic sequestration, and medical intervention (preoperative preparation). However, while chronic blood transfusions can reduce the incidence of sickle cell–induced morbidity and mortality, repeated transfusions result in progressive accumulation of iron in the blood. Excess iron accumulates in organs, particularly the liver and endocrine glands, generating iron-induced morbidity and eventually causing premature death if left untreated. A study in transfusion-dependent patients with SCD demonstrated increased iron deposition, with mean liver iron of 13.68 mg/g dry weight (range of 2.9 to 26.19 mg/g dry weight) and peak mean serum ferritin of $4614 \pm 1989 \,\mu\text{g/L}$ over a transfusion period of $57 \pm 35 \,\mu\text{months}$ (range 12 to 146 months).

In the sickle cell centers of the Cardeza Foundation and Thomas Jefferson University Hospital, approximately 50% of the patients with SCD admitted to the hospital received an average of 10 units of RBCs per year; of these, 17% to 37% developed iron overload. Compared to the non-iron-overloaded group, the iron-overloaded patients with serum ferritin level >1,500 µg/L and transferrin saturation >50% had a higher incidence of painful episodes per year (64% vs. 38%), organ failure (71% vs. 19%), and mortality (64% vs. 5%). Patients who died had significantly higher mean levels of serum ferritin than those who survived (2379 versus 597 μg/L, p<0.05). The results of this study indicate that iron overload is a determinant of morbidity and mortality in adult patients with SCD. (9) Results from a natural history study demonstrated that the unadjusted death rate of transfused patients with SCD (7.0/100 person years) was even higher than in patients with thalassemia (2.2/100 person years). (11) Iron metabolism and trafficking in patients with SCD have some distinctive characteristics. The high levels of inflammatory cytokines in SCD may enhance macrophage/reticuloendothelial cell iron and/or renal cell iron retention. This makes tissues that retain iron different in SCD, and thus the organs that fail due to excess iron load in patients with SCD are somewhat different from those of patients with thalassemia. (12) Indeed, unlike thalassemia patients, cardiac iron overload is not frequently observed in patients with SCD. (13) Nonetheless, cardiac siderosis does occur in some SCD patients who have been transfused for more than 10 years. (14) Care for SCD now commonly uses transfusion, which potentially results in iron overload and necessitates chelation. (12)

1.1.2 Ferriprox®

Ferriprox (deferiprone; active ingredient 3-hydroxy-1,2-dimethylpyridin-4-one) is a bidentate iron chelator that preferentially binds trivalent iron (Fe3+) in a 3:1 (deferiprone : iron) complex.

Its effectiveness has been assessed by urinary iron excretion, sequential measurements of serum ferritin levels, iron concentration in the liver and in the heart, and clinical outcomes such as the ability to prevent iron-induced cardiac disease and prolong survival in transfused patients with thalassemia. Ferriprox was first approved in 1999 by the European Medicines Agency (EMA), and is currently approved in more than 60 countries. In the USA, it was approved in 2011 by the Food and Drug Administration (FDA) for the treatment of patients with transfusional iron overload due to thalassemia syndromes when current chelation therapy is inadequate.

1.2 Rationale

ApoPharma Inc. is currently conducting a 12-month trial, study LA38-0411, to assess the safety and efficacy of deferiprone in patients with SCD or other anemias that necessitate regular blood transfusions (excluding thalassemia syndromes, MDS, myelofibrosis, Diamond Blackfan anemia, and primary bone marrow failure). In that study, a planned 300 participants will be randomized in a 2:1 ratio to receive either deferiprone or deferoxamine. Assessments include weekly, biweekly, or monthly monitoring of absolute neutrophil count (ANC); monthly assessments of adverse events, hematology, biochemistry, and vital signs; quarterly assessments of serum ferritin; and semi-annual serology, ECG, liver iron concentration (LIC) as measured by MRI, cardiac MRI T2*, and quality-of-life questionnaires.

Patients who complete study LA38-0411will be invited to enroll in the current study, LA38-EXT, in which all participants will receive deferiprone. Participants will thus receive deferiprone for a total of either 2 years or 3 years, depending on which treatment was assigned in the earlier study. The long-term data obtained will provide additional information on the safety and efficacy of deferiprone in patients with sickle cell disease or other anemias.

1.3 Potential Risks and Benefits

The safety profile of deferiprone in patients with thalassemia has been extensively characterized. Apart from chromaturia, which is due to iron excretion and is harmless, the most commonly reported adverse events seen in clinical trials have been nausea, vomiting, abdominal pain, increased alanine aminotransferase, arthralgia, and neutropenia. Comprehensive safety information is provided in the US full prescribing information (USPI) and the Investigator's Brochure.

The most significant serious adverse event (SAE) associated with deferiprone use is agranulocytosis, defined as a confirmed absolute neutrophil count less than 0.5×10^9 /L. In

pooled clinical trials, the incidence of agranulocytosis was approximately 2% of patients. The mechanism of deferiprone-associated agranulocytosis is unknown. Agranulocytosis and neutropenia usually resolve upon discontinuation of deferiprone, but there have been some post-marketing reports of agranulocytosis leading to death.

Because of the awareness of this risk, weekly monitoring for neutrophil count was proposed in the first marketing authorization application for deferiprone and has been in effect since. However, a recent review of both clinical and post-marketing data accumulated over the last two decades confirmed that deferiprone-induced agranulocytosis is not dose-related within the therapeutic range, and its occurrence peaks at 5 months after initiation of therapy, declining in frequency after this period. (15) It was concluded that weekly monitoring is a prudent approach but that it does not preclude agranulocytosis from occurring and it could even provide false security, as agranulocytosis could occur shortly after the finding of a normal neutrophil count. The relevance of weekly monitoring of the neutrophil count appears to decrease even further after the first six months of therapy, when agranulocytosis occurs less often. Based upon analysis of data collected over the past 20 years, it appears that patient education may be the key to minimizing risks associated with agranulocytosis during deferiprone therapy. A better approach to minimizing the risks in patients receiving longterm deferiprone therapy is for ANC monitoring to be done weekly only at the beginning of the treatment and to emphasize the importance of educating patients on the need to immediately stop deferiprone and to maintain ANC monitoring upon signs of infection. Based on the conclusions of this review, the frequency of monitoring in this study is reduced: patients who have already been on deferiprone for 12 months in the earlier study, LA38-0411, will now only need to undergo hematology testing monthly, while those who had been on deferoxamine and are now receiving deferiprone for the first time will have their neutrophil count monitored weekly for the first 6 months, biweekly for the next 6 months, and monthly thereafter. Neutropenia management directives (as per Section 7.2.1.8) must be followed at the first sign of neutropenia. Treatment with deferiprone should not be initiated in patients with a history of recurrent neutropenia or an episode of agranulocytosis.

The most common adverse reactions (adverse events assessed as at least possibly related to deferiprone use) seen among the 712 patients treated with deferiprone in ApoPharma clinical trials carried out for the indication of systemic iron overload are listed in the table below. For detailed information on adverse events (AEs) associated with deferiprone, see the Investigator's Brochure. (16)

Adverse drug reactions occurring in $\geq 1\%$ of 712 deferiprone-treated patients

System Organ Class	Patients	
Preferred Term	n (%)	
Blood and lymphatic system disorders		
Neutropenia	49 (6.9)	
Agranulocytosis	15 (2.1)	
Gastrointestinal disorders		
Nausea	89 (12.5)	
Vomiting	69 (9.7)	
Abdominal pain upper	39 (5.5)	
Abdominal pain	23 (3.2)	
Diarrhoea	21 (2.9)	
Dyspepsia	13 (1.8)	
Abdominal discomfort	10 (1.4)	
Investigations		
Alanine aminotransferase increased	54 (7.6)	
Neutrophil count decreased	50 (7.0)	
Weight increased	12 (1.7)	
Aspartate aminotransferase increased	11 (1.5)	
Metabolism and nutrition disorders		
Increased appetite	26 (3.7)	
Decreased appetite	8 (1.1)	
Musculoskeletal and connective tissue disorders		
Arthralgia	75 (10.5)	
Back pain	13 (1.8)	
Pain in extremity	12 (1.7)	
Arthropathy	9 (1.3)	
Nervous system disorders		
Headache	17 (2.4)	
Renal and urinary disorders		
Chromaturia	95 (13.3)	

Data cut-off date: 31 August 2014

Currently, deferoxamine and deferasirox are the only iron chelators licensed for use in patients with sickle cell disease. The benefit to participants in this trial is that they will have the option of being treated with a third chelator.

2 STUDY OBJECTIVES

2.1 Primary Objective

To evaluate the long-term safety and tolerability of deferiprone in iron-overloaded patients with sickle cell disease or other anemias. The endpoints for the primary objective are provided in Section 9.1.1.

2.2 Secondary Objective

To evaluate the efficacy of deferiprone in the treatment of iron overload in patients with sickle cell disease or other anemias who have received deferiprone for up to 3 years.

The endpoints for the secondary objectives are provided in Section 9.1.2.

3 STUDY DESIGN

3.1 Description of Study Design

LA38-EXT is a 2-year prospective, multi-center, single-arm, open-label extension of study LA38-0411. All patients who complete the earlier study will be offered the opportunity to continue in the extension study, with the final visit of LA38-0411 being Visit 1 of LA38-EXT. Patients who had been treated with deferiprone during LA38-0411 (Group 1) will continue to receive deferiprone for an additional 2 years, while those who had been treated with deferoxamine (Group 2) will be switched to deferiprone. Dosage will be 25–33 mg/kg three times a day (t.i.d.).

Patients will have blood counts monitored regularly (monthly throughout the study for patients in Group 1; weekly for the first 6 months, biweekly for the next 6 months, and monthly thereafter for patients in Group 2), and will visit the site quarterly for assessments of safety and efficacy for up to 2 years. The schedule of study procedures is shown in Table 5.1, and details are provided in Section 5.1.

3.2 Rationale for Study Design

This single-arm, open-label extension study design has been primarily chosen to gather information on the safety and efficacy of deferiprone in iron-overloaded patients with SCD or other anemias who have been treated with this chelator for up to 3 years.

3.3 Rationale for Selection of Doses

The dosage of deferiprone for each patient will be between 25 and 33 mg/kg t.i.d., for a total daily dose of 75 to 99 mg/kg. This is the approved therapeutic dose range, and the same as

that being used in study LA38-0411.

Dosing will be as follows:

- Patients who were treated with deferiprone in LA38-0411 will continue on the same dosing regimen in LA38-EXT, unless there has been less than 10% improvement in the last 6 months in at least one of the measures indicative of iron overload (serum ferritin, LIC, or cardiac MRI T2*), in which case the dose can be increased up to 33 mg/kg t.i.d. for patients who were receiving lower doses. If a patient who is already at that dose level is not showing improvement but has consented to participate in the extension study, he/she must remain at 33 mg/kg t.i.d. since that is the maximum permitted.
- For patients who were treated with deferoxamine in LA38-0411, the initial dose of deferiprone will be 15 mg/kg t.i.d. through Week 1, increasing to 20 mg/kg t.i.d. at Week 2 and then to 25 mg/kg t.i.d. at Week 3. It may be further increased to up to a limit of 33 mg/kg t.i.d. if any of the following is true:
 - \circ Transfusional iron input > 0.3 mg/kg/day in the 3 months prior to Visit 1
 - o Serum ferritin ≥2500 μg/L at Visit 1
 - o LIC \ge 15 mg/g dry weight at Visit 1
 - Cardiac $T2* \le 20$ ms at Visit 1

Since the Visit 1 results for the above parameters may not be immediately available, the dosage beyond Week 3 cannot be confirmed at the time when the first supply of drug is dispensed. Details of how dispensing is to be handled at Visit 1 are provided in Section 5.1.

- For any patient, the dose can be increased up to a limit of 33 mg/kg t.i.d. if any of the following is true:
 - At any time during the trial if mean daily transfusional iron input increases to more than 0.3 mg/kg body weight for at least 3 consecutive months
 - o If in the past 6 months there has been less than 10% improvement in at least one of the measures indicative of iron overload (serum ferritin, LIC, or cardiac MRI T2*)
- For any patient, the dose can be decreased at any time during the trial based on assessment of safety markers for adverse reactions that are possibly dose dependent (e.g., gastrointestinal upset, increases in serum liver enzyme levels, and arthropathies).

4 STUDY POPULATION

4.1 Number of Patients

A total of 300 patients are planned to be enrolled in study LA38-0411, and all patients who complete that study will be invited to enroll in the extension study.

4.2 Inclusion Criteria

Patients will be eligible to enroll in study LA38-EXT if they meet all the following criteria:

- 1. Completed study LA38-0411
- 2. Females of childbearing potential must have a negative pregnancy test result at Visit 1. In addition, if applicable, they must:
 - Use an effective method of contraception according to local requirements, during the study and within 30 days following their last dose of study medication, OR
 - Have had a tubal ligation (supporting evidence required), OR
 - Have had a hysterectomy (supporting evidence required), OR
 - Participate in a non-heterosexual lifestyle, OR
 - Have a male sexual partner who has been sterilized (supporting evidence required)
- 3. Fertile heterosexual males and/or their partners must agree to use an effective method of contraception during the study and for 30 days following the last dose of study medication
- 4. All patients and/or their authorized legal representatives must provide signed and dated written informed consent prior to the first study intervention, and assent will be obtained from patients who are considered to be minors. Patients must be able to adhere to study restrictions, appointments, and evaluation schedules.

4.3 Exclusion Criteria

Patients will be excluded from enrollment in study LA38-EXT if they meet **any** of the following criteria:

- 1. Plan to participate in another clinical trial at any time from the day of enrollment until 30 days post-treatment in the current study
- 2. For only those patients who were treated with deferoxamine in study LA38-0411 (Group 2): Presence of any medical condition (including clinically significant laboratory abnormalities, such as ALT ≥ 5 x ULN or creatinine ≥ 2 x ULN), psychological condition, or psychiatric condition which in the opinion of the investigator would cause participation in the study to be unwise.

- 3. Pregnant, breastfeeding, or planning to become pregnant during the study period.
- 4. Treatment failure after 1 year on deferiprone which in the investigator's judgment indicates the need for the patient to be started on a different iron chelator

4.4 Enrolment Violations

The criteria for enrolment must be followed explicitly. If there is inadvertent enrolment of patients who do not meet enrolment criteria, the investigator should consider withdrawing these individuals from the study.

4.5 Patient Withdrawal

Patients have the right to withdraw from the study at any time and for any reason without consequence to future care by the investigator or study center.

A patient may be withdrawn from the study at any time, at the discretion of the investigator, for any of the following reasons:

- Medical or safety reasons considered significant by the patient and/or the investigator
- Requirement for concomitant medication that might interfere with the evaluation of study treatment or may be contraindicated
- Receipt of a rescue medication
- Occurrence of other illnesses that might affect the patient's further participation in the study or evaluation of study treatment
- A protocol deviation that might interfere with study assessments, as judged by the investigator
- Repetitive patient non-compliance with the protocol or with instructions of the investigator
- Participation in another clinical trial at any time during the conduct of this study
- Any other situation where, in the opinion of the investigator, continuation of the study would not be in the best interest of the patient

A patient **must** be withdrawn from the study if any of the following conditions apply:

 Pregnant or planning to become pregnant (see Section 7.2.4, Procedures in Case of Pregnancy)

- Occurrence of any adverse event characterized as life-threatening or disabling that is not associated with the patient's condition
- A confirmed ANC $< 0.5 \times 10^9$ /L. (For the potential withdrawal of patients with ANC between 0.5 and 1.5 x 10^9 /L, see Section 7.2.1.8.)
- Non-compliance with blood counts:
 - o Group 1: Missing 2 consecutive monthly blood counts will result in automatic withdrawal. If a patient misses one of the scheduled quarterly visits at which hematology testing would normally be done, an unscheduled visit for hematology testing must be completed within 10 days of the missed visit.
 - o Group 2: For the first 6 months, if a patient misses a weekly blood count visit, then missing a further 3 of the next 5 visits (i.e., a total of 4 out of 6) will result in automatic withdrawal. For the next 6 months, missing 3 consecutive biweekly blood counts will result in automatic withdrawal. For the remainder of the study, missing 2 consecutive monthly blood counts will result in automatic withdrawal. As with Group 1 patients, if a patient misses one of the scheduled quarterly visits, an unscheduled visit for hematology testing must be completed within 10 days of the missed visit.
- Termination of the study by the sponsor

Patients who decide to withdraw participation in the study should always be contacted, if possible, in order to ask about the reason for withdrawal, whether any adverse events (AEs) occurred, and use of concomitant medications. A withdrawn patient should return for an Early Termination Visit and a follow-up visit. All investigational product and materials should be returned. If any AEs occurred, the investigator must attempt to follow up the outcome for 30 days post-termination.

If a patient withdraws or is withdrawn before completing the study, the date and reason for the withdrawal must be entered on the source document and on the appropriate page of the case report form (CRF), and all other appropriate CRF pages must be completed.

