4.7 Rescue Medication

Rescue medication (deferoxamine, or a combination of 2 iron chelators: deferiprone, deferoxamine, or deferasirox) for the treatment of iron overload will not be allowed during the study. Should symptoms become intolerable for a patient, dose adjustment should be attempted. If the treatment is unsuccessful, the investigator may decide to withdraw the patient from the study in order to optimize treatment.

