9.3 Study Populations

Study populations intended for analysis will be defined as follows: Intent-to-Treat (ITT), Per-Protocol (PP), and Safety. The ITT population will represent the primary analysis population to evaluate all efficacy endpoints. The efficacy endpoints will also be analyzed for the PP population, which is the secondary analysis population.

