6.2.1 Intent-to-Treat Population

The ITT population will include all randomized patients who received at least one dose of study drug and have a baseline and at least one post-baseline efficacy assessment.

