6.2.2 Per Protocol Population

The Per-Protocol (PP) population will include all enrolled patients who complete the study, have no major protocol violations, and have an efficacy assessment at the end of the study. Prior to database lock, patients with major protocol violations will be reviewed and excluded, where appropriate, from the PP population. Major protocol violations will include (but not be limited to) the following:

- Patients who were not compliant with the treatment (<80% compliance)
- Patients who took iron chelator medications other than the assigned study medication during the course of the study

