6.3.3 Analysis of Efficacy

Changes in LIC, in cardiac MRI T2*, and in serum ferritin from baseline to Year 1 (both groups; Group 1 data are from LA38-0411), from baseline to Year 2 (both groups), and from

baseline to Year 3 (Group 1 only) will be summarized with descriptive statistics and will be tested against no change using a one-sample t-test. The changes in these 3 efficacy measures from the start of deferiprone therapy to the last visit of LA38-EXT in all patients, irrespective of whether deferiprone therapy was initiated in LA38-0411 or in LA38-EXT, will also be tested using a one-sample t-test. In addition, the percentages of responders will be tabulated for Year 1 (both groups; Group 1 data are from LA38-0411), for Year 2 (both groups), and for Year 3 (Group 1 only) of deferiprone therapy. The change from baseline to end of LA38-041 for deferoxamine and the change from baseline to end of LA38-EXT for deferiprone in Group 2 will be compared.

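### The primary efficacy tests have no rule for values taken after a chelator other than deferiprone, so any improvement from that chelator is credited to deferiprone

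*Protocol*

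**What the plan says.** **Rescue and withdrawal.** Protocol 4.7 states that rescue chelation "for the treatment of iron overload will not be allowed during the study". It adds that, if treatment does not succeed, "the investigator may decide to withdraw the patient from the study in order to optimize treatment". Protocol 4.5 places "Receipt of a rescue medication" under the lead-in "A patient may be withdrawn from the study at any time, at the discretion of the investigator, for any of the following reasons". The separate list of mandatory withdrawal reasons in 4.5 does not include it.

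**Analysis sets.** Protocol 9.3 states: "The ITT population will represent the primary analysis population to evaluate all efficacy endpoints". SAP 6.2.1 defines that set as "all randomized patients who received at least one dose of study drug and have a baseline and at least one post-baseline efficacy assessment". SAP 6.2.2 defines the per-protocol (PP) set, which is secondary for efficacy. It requires completion and an end-of-study assessment, and names as a major violation "Patients who took iron chelator medications other than the assigned study medication during the course of the study". Violators are removed only where the review before database lock judges it appropriate.

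**Tests.** SAP 6.3.3 uses one-sample t-tests of change against zero at each year of therapy. It adds a test of change "from the start of deferiprone therapy to the last visit of LA38-EXT in all patients", and responder percentages. Protocol 9.5 keeps patients who withdrew early eligible for the efficacy analyses.

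**The concern.** The secondary objective is the efficacy of deferiprone. A one-sample test attributes the whole observed change to the study drug, because no concurrent arm exists in which other chelators would also be used. If a patient takes deferoxamine or a combination and later has a lower LIC or ferritin, or a higher T2*, that change enters the mean and the responder count as though deferiprone had produced it. Protocol 4.7 links departure from the regimen to unsuccessful treatment, so the patients affected are plausibly those doing worst on deferiprone. Poor responses could then be recorded as improvement in the set designated primary for efficacy.

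**Working it through.** **Step 1: look for a rule.** Neither SAP 6.2.1 nor SAP 6.3.3 says that a value after another chelator is to be excluded, set to missing, imputed or counted as non-response. Protocol 9.3.1 and 9.4.1.3 do not say so either. As written, all such values are used.

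**Step 2: locate the cause.** Suppose withdrawal after rescue were automatic. Protocol 9.5 would still keep the patient eligible for efficacy. Table 5.1 schedules liver MRI, cardiac T2* and ferritin at the Early Termination visit, which Protocol 5.1 allows up to one month after the last dose. A value obtained after another chelator could still be that patient's last-visit value. The discretionary wording in 4.5 lets more such values arise, but the gap itself is the missing data rule in the SAP.

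**Step 3: see whether PP closes it.** PP can remove the users of other chelators. It removes each of them entirely, including sound earlier values, and it also removes every non-completer. No planned analysis uses values on deferiprone alone from all treated patients.

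**Step 4: illustrate the size.** The documents state no rescue rate, SD, significance level or power for this extension, so there is no plan figure to reproduce.

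*From the documents:* 300 patients planned in the parent study, randomized 2:1 (Protocol 1.2 and 9.2). The ceilings are 300 × 2/3 = 200 in Group 1 and 300 × 1/3 = 100 in Group 2.

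*Assumed:* SD of LIC change s = 5 mg/g; true deferiprone change zero; a fraction f of patients has an extra fall d of 4 to 6 mg/g from another chelator; two-sided 5% test, so 2.5% in the favorable direction.

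- Shift in the mean fall = f × d
- Variance = s² + f(1 − f)d²
- Noncentrality = shift / √variance × √n
- Chance of a significant fall = probability that a noncentral t on n − 1 degrees of freedom exceeds the 97.5% point of the central t

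Example with f = 5%, d = 6, n = 200:

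- Shift = 0.05 × 6 = 0.30 mg/g
- Variance = 25 + 0.05 × 0.95 × 36 = 26.71, so SD = 5.168
- Noncentrality = 0.30 / 5.168 × 14.142 = 0.821
- Critical value 1.972; chance 12.7%

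| Share on another chelator | Mean shift, mg/g (d = 4 to 6) | Chance of significant fall, n = 200 | n = 100 |
|---|---|---|---|
| 2% | 0.08–0.12 | 4.1–5.2% | 3.6–4.2% |
| 5% | 0.20–0.30 | 8.0–12.7% | 5.8–8.3% |
| 10% | 0.40–0.60 | 19.4–35.5% | 11.7–20.0% |

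All are to be read against 2.5%. The shift does not depend on n; the false-positive chance does.

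**The case against.** A reader might infer that 4.5 and 4.7 flatly contradict each other and that this contradiction causes the bias. The documents do not support that. A drug can be prohibited while withdrawal after its use is left to judgment, and 4.7 itself uses discretionary wording. The two sections are in tension, and Step 2 shows that mandatory withdrawal would not remove the values.

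It can also be said that the plan steers such patients away. Exclusion criterion 4 bars patients whose failure on deferiprone calls for a different chelator, Protocol 3.3 permits dose increases within its stated limit, and 4.7 points to dose adjustment and then possible withdrawal. Nothing in the documents supports a share of 5% or 10%. This stands, and it is why the 2% row belongs beside the others. Also, n = 200 assumes that every Group 1 patient completes the parent study and enrolls.

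PP names use of other chelators, and Table 14.3.4.1 would show users by drug. Both help. Neither provides an estimate on deferiprone alone that keeps non-completers.

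The most useful objection concerns the remedy. LIC and T2* are measured in the extension only at Visits 1, 5 and 9. Simply cutting values at the other chelator would drop a Group 2 patient who starts one before Week 52, and would take any patient who starts one before Week 104 out of the final-year test. If these are the failures, plain truncation could itself favor deferiprone. This stands, and the fix below allows for it.

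**Conclusion.** The concern holds as a gap in the SAP: the primary efficacy tests and responder rates credit to deferiprone any change that follows another chelator, and the PP analysis protects only in part. It bears on the secondary objective; the primary objective is safety. On the stated assumptions, at n = 200 the effect is small at about 2% of patients and material at about 10%. It is conditional on such use occurring, and the documents do not show that it did or how often. A reader might infer that the efficacy results are in fact inflated; nothing in the documents supports that. The figures rest on an assumed SD, fall, share and significance level, and on a true deferiprone effect of zero.

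**What to change.** In SAP 6.3.3, keep the ITT tests and add:

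- **Yearly tests:** the same tests for LIC, T2* and ferritin using only values up to the first dose of any chelator other than deferiprone, with no completion requirement.
- **Last-visit test:** for each patient who took another chelator, use the last value before that dose.
- **Responder tables:** count these patients as non-responders from that dose on, so that they stay in the denominator.
- **Reporting:** give the number of patients and values affected, and separately the number with no post-baseline MRI value before the other chelator.

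The sponsor should reconcile Protocol 4.5 and 4.7; which rule applies is not a matter for this review.

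The cost is a few SAP sentences and one supplementary run. Protocol 7.2.3.4 already collects medication start and stop dates, and listing 16.2.21 holds the medication data. The downside is that the yearly MRI tests lose some values and the loss is informative, since it is likely to fall on patients doing badly; the report should say so. Ferritin, measured quarterly, should lose less. If no patient took another chelator, one sentence closes the point.
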